2.0 Rationale and Specific Aims

Acute kidney injury (AKI) is a devastating complication following cardiac surgery. Five hundred thousand people undergo cardiac surgery each year in the U.S.,⁵ and AKI complicates recovery in up to 30% of these patients, requiring renal replacement therapy (dialysis) in 1-4%.⁶⁻⁹ AKI is associated with postoperative arrhythmias, wound infections, and sepsis, and AKI independently predicts a 5-fold increase in death at 30 days.¹⁰⁻¹³ We have demonstrated that F_2 -isoprostanes, products of arachidonic acid peroxidation that have emerged as the gold standard for the measurement of oxidative stress *in vivo*,¹⁴ increase significantly *during* cardiac surgery and independently predict an increased incidence of AKI.¹ Isofurans are products of arachidonic acid peroxidation formed preferentially over F_2 -isoprostanes under conditions of increased oxygen tension,¹⁵ and we have found that isofurans increase to a greater extent than F_2 -isoprostanes during cardiac surgery and are associated with AKI.¹⁶ Hyperoxia increases production of ROS *in vitro* and in rodents,¹⁷ and in recent clinical studies hyper-oxygenation during resuscitation from cardiac arrest independently predicted persistent coma and death.^{3,4,18} In preliminary studies, we found that cardiac surgery patients are exposed to oxygen concentrations well above those required to maintain hemoglobin oxygen saturation (median arterial partial pressure of oxygen [PaO_2] = 364 mmHg during surgery) and reducing excess oxygen exposure reduces both F_2 -isoprostanes and isofurans. Moreover, reducing excess oxygen exposure was associated with less postoperative renal injury.

We hypothesize that physiologic oxygenation during surgery decreases the generation of reactive oxygen species, decreases oxidative damage, and decreases kidney dysfunction following cardiac surgery compared to hyper-oxygenation. To test this hypothesis we propose the following **SPECIFIC AIMS**:

Aim 1: Test the hypothesis that maintaining physiologic oxygenation during anesthesia for cardiac surgery decreases postoperative kidney injury.

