We will recruit and randomize 200 cardiac surgery subjects to hyper-oxygenation ($\text{FIO}_2 = 0.8-1.0$, usual care) or physiologic oxygenation (minimum FIO_2 required to saturate arterial hemoglobin 95-97% and maintain a PaO_2 between 80-110 mmHg) during surgery. We will compare postoperative changes in serum creatinine and markers of nephron injury (neutrophil gelatinase-associated lipocalin [NGAL], between subjects randomized to physiologic oxygenation or hyper-oxygenation to test the hypothesis that maintaining physiologic oxygenation during anesthesia for cardiac surgery decreases postoperative kidney injury. To assess tissue oxygenation in the two study groups, we will continuously measure (automatically recorded every 5 seconds) the FIO_2 , SpO_2 , brain O_2 saturation, and muscle O_2 saturation. In addition, we will measure the PaO_2 , cardiac output, and arterial lactate prior to, during, and following surgery but no less frequently than every hour. We will compare these oxygenation metrics between subjects randomized to hyper-oxygenation vs. physiologic oxygenation to assess oxygen delivery and

consumption between groups. The primary endpoints of Aim 1 will be serum creatinine change (median +/- 95% confidence interval (CI)). Secondary endpoints include additional measures of AKI (incidence of AKI [defined using KDIGO criteria], neutrophil gelatinase-associated lipocalin [NGAL], and insulin-like growth factor-binding protein 7 [IGFBP7]/tissue inhibitor of metalloproteinases-2 [TIMP-2]), incidence of delirium (measured using CAM-ICU), duration of mechanical ventilation, duration of hospitalization, SpO₂ (median +/- 95% CI and area-under-the-curve (AUC) < 90%), PaO₂ (median +/- 95% CI, AUC > 150 mmHg, and AUC < 70 mmHg), brain and muscle O₂ saturation (median +/- 95% CI and AUC < 80% baseline), and the percent of FIO₂ titrations within protocol (protocol adherence). Safety endpoints will focus on any risk of hypoxia between study groups and will include postoperative serum CK-MB measurements and rates of arrhythmias, reintubation, transient ischemic attack, stroke, and death.

Aim 2: Test the hypothesis that physiologic oxygenation during cardiac surgery reduces the generation of superoxide (measured by electron paramagnetic resonance of CAT-1H and TMH electron spin probes) and systemic oxidative stress (measured by plasma concentrations of F₂-isoprostanes and isofurans).

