5.0 Enrollment/Randomization/Blinding

Patients scheduled for open-heart surgery will be screened via StarPanel. Research personnel will request an introduction from the subject's physician. If the subject agrees to the introduction, research personnel will meet with eligible study candidates during their preoperative surgical and / or anesthesia clinic appointment or on the hospital ward. Following explanation of the protocol and documented

informed consent, patients will be randomized to 1) usual care (administration of 100% FIO₂ during surgery and 80% inspired oxygen during cardiopulmonary bypass) or 2) maintenance of physiologic oxygenation (the minimum FIO₂ required to maintain SpO₂ of 95%, but no less than that of air [21%]) during surgery. The intervention is restricted to intraoperative patient management, and upon admission to the ICU after surgery all patients will be ventilated with 40% FIO₂ or the minimum required to maintain SpO₂ 95% if greater than 40%. Regardless of treatment group, all subjects will receive 100% oxygen during induction of anesthesia until tracheal intubation and lung ventilation are verified and during transport from the operating room to the ICU. Patients, laboratory technicians, statisticians and ICU staff but not anesthesiologists, perfusionists, and respiratory therapists will be blinded to treatment group. Preoperative, intraoperative, and postoperative care will remain unaffected by inclusion in this study or by study group assignment aside from administration and monitoring of oxygenation.

The study's statistician will be responsible for centralized randomization and subject assignment based on stratification in a permuted block fashion, using a sequence of blocks with sizes either two or four, where the sizes are selected uniformly at random. Randomization will be stratified by chronic kidney disease (defined as stage 3, 4, or 5 CKD [i.e., an eGFR <60 ml/min/1.73m²]) and use of cardiopulmonary bypass during surgery.

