- Following induction of anesthesia and verification of tracheal intubation and lung ventilation, subjects will be ventilated with 21% oxygen with a tidal volume of 8 ml/kg ideal body weight, respiratory rate titrated to an end-tidal partial pressure of CO₂ of 35 cm H₂O, and positive end-expiratory pressure of 5 mmHg. FIO₂ during lung ventilation may be increased and subsequently decreased in order to maintain SpO₂ between 95-97 % (see "Titration of FIO₂ during surgery" below).
- During initiation of cardiopulmonary bypass, the oxygenator in the cardiopulmonary bypass circuit will be ventilated with 60% FIO₂ and the gas flow titrated to achieve an arterial blood partial pressure of CO₂ of 50 mmHg. Immediately following achievement of full flow on cardiopulmonary bypass, the FIO₂ will be decreased to achieve a SpO₂ between 95-97%, and an arterial blood gas sample will be measured to titrate the inline co-oximeter. Subsequent FIO₂ titrations during cardiopulmonary bypass will be made using the inline co-oximeter to achieve target PaO₂ 80-110 mmHg (see "Titration of FIO₂ during surgery" below).
- During transport from the operating room to the ICU following surgery, subjects will be connected to an Ambu bag and mechanically ventilated with 6 liters oxygen per minute fresh gas flow (similar to hyper-oxygenated group subjects).
- Upon arrival in the ICU subjects will be placed on the ICU ventilator and ventilated with 40% oxygen or the same FIO₂ the patient was being ventilated at the completion of surgery (whichever is higher), with a tidal volume of 8 ml/kg ideal body weight, respiratory rate of 12 breaths per minute, and positive end-expiratory pressure of 8 mmHg.
- Subsequent mechanical ventilation, supplemental oxygen administration, and subject extubation will be at the discretion of the ICU intensivist.

Titration of FIO₂ during surgery (for both the hyper-oxygenation and physiologic oxygenation groups):

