Throughout the course of intervention, which runs from post anesthetic induction to transfer of care to the ICU staff, the subject's anesthesiologist will continuously monitor the subject's SpO₂ with every beat of the heart, as is standard care. During cardiopulmonary bypass the subject's perfusionists will continuously monitor the subject's PaO₂ with real-time inline co-oximetry, as is standard care. Anesthesiologists and perfusionists are intimately familiar with monitoring patient oxygenation and titrating oxygen delivery. The maintenance of perfusion and tissue oxygen delivery is the most basic responsibility of anesthesiologists and perfusionists.

During lung ventilation, if a subject's SpO₂ falls below 95% for 1 minute, the anesthesiologist will increase the FIO₂ by 10%. If the SpO₂ rises to > 97%, the anesthesiologist will decrease the FIO₂ by 10%. If the anesthesiologist determines the subject requires more than a 10% change in FIO₂, the adjustment of the FIO₂ is at the discretion of the anesthesiologist. The anesthesiologist will wait 2 minutes between changes in FIO₂ unless the anesthesiologist determines the subject requires more rapid titration of FIO₂ to maintain target SpO₂ 95-97%. A fresh gas flow of 2 liters/minute will be maintained throughout surgery.

During cardiopulmonary bypass, if a subject's arterial oxygen tension falls below 80 mmHg, the perfusionist will increase the FIO₂ by 10%. If the SpO₂ rises above 110 mmHg, the perfusionist will decrease the FIO₂ by 10%. If the anesthesiologist or perfusionist determines the subject requires more than a 10% change in FIO₂, the adjustment of the FIO₂ is at the discretion of the anesthesiologist and perfusionist. The perfusionist will wait 2 minutes between changes in FIO₂ unless the anesthesiologist or perfusionist determines the subject requires more rapid titration of FIO₂ to maintain target PaO₂ 80-110 mmHg.

We will evaluate the following endpoints (primary, secondary, and safety endpoints):

1. Postoperative creatinine change from baseline to postoperative day 2 (Aim 1 primary endpoint). Serum creatinine will be measured daily during hospitalization.
2. Additional markers of AKI including incidence of AKI using KDIGO criteria and urinary markers NGAL and IGFBP-7/TEMP-2.²⁴
3. Incidence and duration of delirium, measured using the Confusion Assessment Method for the ICU (CAM-ICU) twice daily while in the ICU or for at least 3 days postoperatively.²⁵

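### The FIO2 titration rules are headed as covering both arms, but their decrease orders and targets describe the physiologic arm and contradict the control regimen

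*Combined protocol and SAP*

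**What the plan says.** Section 6.0 (Study Procedures) first gives a list of bullets for each arm, then a shared block on titration, headed as applying "during surgery (for both the hyper-oxygenation and physiologic oxygenation groups".

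The shared block has one paragraph per phase, and neither distinguishes the arms:

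- Lung ventilation: "If the SpO₂ rises to > 97%, the anesthesiologist will decrease the FIO₂ by 10" percent. Faster changes are allowed if the patient "requires more rapid titration of FIO₂ to maintain target SpO₂ 95-97" percent.
- Bypass: "If the SpO₂ rises above 110 mmHg, the perfusionist will decrease the FIO₂ by 10" percent. Faster changes are allowed if the patient "requires more rapid titration of FIO₂ to maintain target PaO₂ 80-110 mmHg".

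Each paragraph also has an increase rule, triggered by SpO2 below 95% or arterial oxygen tension below 80 mmHg.

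The control regimen appears in three places. Section 5.0 describes it as "usual care (administration of 100% FIO₂ during surgery and 80% inspired oxygen during cardiopulmonary bypass". Section 2.0, Aim 1, gives an FIO2 range of 0.8-1.0. The control bullets in section 6.0 set 100% in lung ventilation and 80% on bypass. The only adjustment they mention is an increase on bypass, for which they point to the shared block.

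Two analyses depend on what counts as following the protocol. Section 2.0 and item 4 of the section 6.0 endpoint list make the share of FIO2 titrations that follow the protocol an endpoint. Section 10.0 (Data Analysis Plan) calls for violators to be identified before unblinding, with a secondary per-protocol analysis.

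**The concern.** A control kept at the assigned FIO2 complies with the control bullets. If that patient's SpO2 is above 97%, or PaO2 on bypass is above 110 mmHg, the same conduct breaches the shared block. The protocol does not say which text governs, and it gives no adherence definition specific to controls.

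Two things are at stake. The first is the instruction for delivering the intervention: obeyed as written, it would move controls toward the physiologic targets and erode the randomised contrast. The second is the scoring of controls, because whoever draws up the violator list has two written standards that disagree.

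**Working it through.** No figure in the plan is at issue, so the check is a comparison of texts followed by a short count of steps.

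**1. The rules side by side**

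| Phase | Control regimen (2.0, 5.0, 6.0 control bullets) | Physiologic regimen (6.0 bullets) | Shared block, headed for both |
|---|---|---|---|
| Lung ventilation | 100%; no titration mentioned | Start at 21%; up and down to SpO2 95-97% | Up below SpO2 95%, down above 97% |
| Bypass | 80%; increase only | Start at 60%; titrate to PaO2 80-110 mmHg | Up below 80 mmHg, down above 110 mmHg |

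The shared block's targets match the physiologic column in both rows. The control column has no decrease and no upper limit.

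**2. Which part of the block can apply to controls**

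The control bypass bullet cites the block for increases, so the heading is not simply a slip: the bypass increase rule is meant for controls. In lung ventilation a control already at 100% cannot be increased, so the only order that could act on that patient is the decrease. If bypass FIO2 is raised for a control, no control-specific rule says when or how far it comes back down.

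**3. The misprint**

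The bypass trigger gives a saturation in mmHg. The 80 mmHg arterial tension trigger and the PaO2 target in the same paragraph show that PaO2 is meant.

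**4. Steps needed to leave the control range if the block is obeyed literally**

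Inputs: starting FIO2 of 100% and 80% (5.0, 6.0), steps of 10% (6.0), lower limit of 0.8 (2.0, Aim 1).

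- Step as 10 percentage points. Bypass: 80 → 70, below 80 after 1 step. Lung ventilation: 100 → 90 → 80 → 70, below 80 after 3 steps.
- Step as 10% of the current value. Bypass: 80 × 0.9 = 72, below 80 after 1 step. Lung ventilation: 100 → 90 → 81 → 72.9, below 80 after 3 steps.

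The count is the same on either reading. In lung ventilation the first step already departs from the 100% assigned in sections 5.0 and 6.0. No elapsed time is claimed, because the block allows larger and faster changes at the clinicians' discretion.

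**The case against.** The strongest reply is that the document resolves the conflict when read as a whole. Each arm's bullets say what that arm takes from the shared block: the control bypass bullet takes increases, the control lung-ventilation bullet takes nothing, and the physiologic bullets take titration in both directions and the targets. Three sections agree on high oxygen for controls. Under section 5.0 the anesthesiologists and perfusionists know the assignment and deliver it. On this view the defect is a loose heading.

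Most of that stands. A reader might infer from the literal rule that controls will be titrated down, with loss of contrast and power. The documents do not support that as an expectation, since unblinded staff with a clear control regimen would probably not do it.

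The adherence endpoint is also largely safe. A titration is most naturally a change that was made, so a control left at the assigned FIO2 contributes none, and an omitted decrease does not count against that patient. The endpoint is affected only if omissions are scored.

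It can also be said that nobody would strike controls from the per-protocol set for receiving their assigned oxygen. That is likely, but it relies on the person making the list to choose the sensible standard when the protocol states two. Knowledge of the assignment in the operating room does not settle how violations are scored later.

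**Conclusion.** The inconsistency is real as written: a rule stated for both arms contradicts the control regimen, and no text exempts controls. Its likely effect is small. The primary intention-to-treat analysis is probably unaffected, on the assumption that staff follow the arm-specific bullets. What remains is uncertainty over the standard for naming control violators in a secondary analysis.

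The size can be stated only as the step count: one step on bypass or three in lung ventilation takes a literally managed control below 0.8.

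A reader might go further and infer that at least half of the controls would count as deviating, because section 2.0 reports a "median arterial partial pressure of oxygen [PaO_2] = 364 mmHg during surgery", which is 364 / 110 = 3.3 times the bypass trigger. That does not follow. The median comes from preliminary patients and covers surgery as a whole, whereas the 110 mmHg trigger applies only on bypass, where controls receive 80%. Off-pump patients are enrolled and never meet that trigger. In lung ventilation the trigger is SpO2, and the text gives no figure for how often controls exceed 97%. No count of affected controls can be supported from the documents.

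**What to change.** Amend the titration block in section 6.0 as follows:

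- Limit the decrease orders and the upper limits of the targets to the physiologic arm.
- For controls, state FIO2 100% in lung ventilation and 80% on bypass, raised on bypass if PaO2 falls below 80 mmHg and then returned to no less than 80%. The return rule is new content, but the present text leaves that step undefined for controls.
- Correct the bypass trigger from SpO2 to PaO2.

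In section 10.0, state that adherence and violations are scored by these arm-specific rules, fixed in advance. Section 5.0 withholds the treatment key from investigators and statisticians until the dataset is locked, and the violator list is due before unblinding. The rules should therefore be applied by someone who holds the key and is not an analyst. That person should pass on only the violator status, because the FIO2 records would largely reveal the arm.

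The cost is a few sentences of amendment and a named key-holder for scoring. FIO2, SpO2 and PaO2 are already recorded, so no extra patients or measurements are needed.

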11. One year follow-up data including assessments of cognitive function (Short Blessed Test), activities of daily living, and depression (Center for Epidemiologic Studies-Depression (CES-D) test will be obtained by phone interview, and we will examine the clinical chart for admissions, events (any renal replacement therapy), and laboratory findings (with particular focus on serum creatinine, eGFR, and urine proteinuria) in this period.
12. Safety endpoints will focus on any risk of hypoxia between study groups and will include postoperative day 1 serum CK-MB measurements (myocardial injury, defined as CK-MB greater than 50 ng/mL [10 times the upper limit of normal] and CK-MB as a continuous endpoint), postoperative myocardial infarction [defined by a new Q-wave on EKG], rates of reintubation, transient ischemic attack [defined as new deficit on neurologic exam that abates within 72 hours], stroke [defined as new deficit on neurologic exam and confirmed with radiological evidence], and death.

Urine, blood, and tissue use:

Following the placement of the arterial line and Foley catheter, 20 mL of blood and 20 mL of urine will be collected at the induction of anesthesia (baseline). We will also collect 15 mL blood and 20 mL of urine during cardiopulmonary bypass or off-pump coronary artery bypass for those subjects not requiring cardiopulmonary bypass, following cardiopulmonary bypass or off-pump coronary artery bypass, at ICU admission, 6 hours after ICU admission, and on postoperative day 1 and day 2. In total we will collect 110 mL of blood and 140 mL urine. When, after dissection of the pericardial fat, mammary artery, and incision of the atria as part of standard cardiac surgery, 1-2 g of redundant atrial tissue, 1-2 grams of discarded fat, and 1-2 g of discarded distal mammary artery will be collected for measurement of atrial myocardial function, inflammation, amyloid, oxidative stress, and arteriole vascular reactivity. Typically, this tissue is discarded, but instead we will harvest this tissue at the end of surgery. We used the same technique for collection of tissue in 450 cardiac surgery subjects in the Atrial Fibrillation and Renin Angiotensin Aldosterone System (RAAS) study (PI: [name]).²⁶

We will also collect data regarding vital signs, electroencephalographic activity, medication use, fluid input and urine output, clinical labs, and postoperative outcomes.

Sample Time-course:

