- Preoperative: The PI or his research nurse will offer study participation to adult patients

undergoing cardiac surgery after patients express interest to their surgeon in conjunction with a patient's preoperative surgical consultation appointment, preanesthetic evaluation appointment, or on the hospital ward. We successfully recruited subjects in these venues for 653 patients enrolled in the Statin AKI Cardiac Surgery RCT (PI: [name]).²⁷ After obtaining informed consent, patients will undergo a brief neuropsychological assessment that will include the Mini Mental Status test, the Trails B test, the CES-D Test, and the NRS 0-10 pain assessment. Patient demographics and past medical history will be documented.

- Day of surgery: anesthesia, surgery, and ICU admission will proceed irrespective of the subject's participation in the study except for the oxygen administration and monitoring and sample collection described above. Study intervention will occur in the operating room and will terminate when subject care is transferred from the anesthesiologist to the intensivist following admission to the ICU.
- Postoperative: subject postoperative ICU and hospital ward stay will proceed irrespective of the subjects' participation in the study and will be controlled by the subject's surgeon, intensivist, and consultants. Patients will be evaluated twice daily while in the ICU or for the first 3 days following surgery for level of sedation using the Richmond Agitation-Sedation Scale (RASS)²⁸ and for delirium using the CAM-ICU. Both of these assessments are standard practice in the ICUs at VUMC. On postoperative day 5 we will assess patients pain using the NRS 0-10 pain scale and the short-form McGill Pain Questionnaire.
- Subject discharge will proceed irrespective of study. In the Statin AKI Cardiac Surgery RCT, median hospital length of stay was 7 days.
- One year following surgery, we will call patients to conduct a phone interview in which we will assess neuropsychological function and activities of daily living including NRS 0-10 pain scale, short-form McGill Pain Questionnaire, the Short Blessed Test, and the CES-D Test. This assessment will take about 15 minutes to complete.

Data and Safety Monitoring Board (DSMB):

The DSMB will provide objective review of the treatment results as they relate to human safety and data quality. [REDACTED] have agreed to serve on the committee. [REDACTED], who will serve as chair, is [REDACTED]

[REDACTED]

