We will use the Perioperative Data Warehouse (PDW), an IRB-approved research registry, and the Enterprise Data Warehouse (EDW) to extract additional clinical data. Vanderbilt's electronic healthcare records are stored in the EDW and Vanderbilt's Department of Anesthesiology healthcare records are stored in the PDW. The EDW is an electronic repository of clinical and administrative information, which is updated daily. It stores diverse sources of data from scheduling and billing systems, patient registries, nursing documentation, inpatient and outpatient clinical documentation, computerized order entry systems, pharmacy medication administration records, laboratories, radiological studies, and mortality data from the Social Security Administration Death Master File. Clinical data extracted from the PDW and the EDW data may include but are not limited to demographics (i.e., age, gender, ASA physical status, weight, height, BMI), procedures performed and associated process times (i.e. start of procedure, end of procedure, entry into pacu, discharge from pacu), type of anesthesia associated with procedures, preadmission medications, medications administered during hospital admission, laboratory data (i.e. troponin, CK-MB, creatinine, etc), physiologic information (i.e. vital signs, ventilator data, etc), diagnoses, medical history & co-morbidities, patient allergies, clinical indicators (post-operative pain scores, PONV scores, etc.), medical record (StarPanel) notes regarding any rapid response/code calls, ICU transfers, or in-hospital deaths, and clinical outcomes (i.e., hospital length of stay, mortality, ICU admission, unexpected ICU admission, rapid response/code calls, hospital readmissions, ER visits, etc.) and associated dates.

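### One-year admissions and renal replacement therapy come from the institution's own records, and the planned one-year call lists no question on either, so events treated elsewhere may be missed

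*Combined protocol and SAP*

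**What the plan says.** Endpoint 11 in section 6.0 (Study Procedures) divides the one-year data by source. Cognition, daily living and depression "will be obtained by phone interview". For the remainder, "we will examine the clinical chart for admissions, events (any renal replacement therapy), and laboratory findings", with particular attention to kidney laboratory values.

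The time-course in the same section describes the call: "One year following surgery, we will call patients to conduct a phone interview". The instruments it names are the "NRS 0-10 pain scale, short-form McGill Pain Questionnaire, the Short Blessed Test, and the CES-D Test", alongside daily living, and "This assessment will take about 15 minutes to complete". Hospital admission and dialysis are not listed.

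Section 11.0 (Privacy/Confidentiality Issues) adds extraction from two data warehouses. The variables include "hospital readmissions, ER visits, etc", but the warehouses hold the institution's own data: "Vanderbilt's electronic healthcare records are stored in the EDW". The one external source named is a federal death file, which covers mortality only.

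The missing-data paragraph in section 10.0 is general. It allows imputation as a sensitivity analysis and does not address one-year events.

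**The concern.** A chart shows only what reaches it. If a patient returns to local care after surgery and is admitted or starts dialysis at another hospital, the institution's chart and warehouses may show nothing. That record looks the same as the record of a patient who stayed well. The plan gives no way to tell the two apart: it has no definition of observed follow-up, no request for outside records and no classification rule for patients without one-year contact. The general missing-data text does not help, because an event absent from the chart is not flagged as missing.

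Kidney injury is the trial's central clinical question, and endpoint 11 is where kidney outcomes are followed to one year. Low one-year rates could mean few events or care received elsewhere, and the trial as planned could not say which. The plan already includes a one-year telephone contact that could supply the information.

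**Working it through.** The plan gives no one-year event rate and no share of patients followed elsewhere, so there is no figure to reproduce. The steps below set the sources side by side and then show how the size depends on assumed inputs.

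**1. Which source could show an event at another hospital?**

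| Source | Admissions | Renal replacement therapy | Reaches other hospitals? |
|---|---|---|---|
| Clinical chart (6.0, endpoint 11) | yes | yes | only if later noted in the chart |
| Data warehouses (11.0) | yes | not listed by name | described as the institution's own records |
| Death file (11.0) | no | no | yes, for deaths only |
| One-year call (6.0, time-course) | not listed | not listed | could, if asked |

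**2. Undercount if unseen events are coded as no event.** Let f be the share of events not visible. Observed rate = (1 − f) × true rate, and an absolute difference shrinks by the same factor if f is equal in both arms. Assumptions: 200 patients and a true one-year admission rate of 30%, so 0.30 × 200 = 60 events.
- f = 15%: 0.85 × 60 = 51 seen
- f = 30%: 0.70 × 60 = 42 seen
- f = 50%: 0.50 × 60 = 30 seen

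**3. Why the classification rule matters.** Suppose 30% of the 200 patients (60) are wholly unobserved and have the same 30% event rate as the others. The 140 observed patients have 0.30 × 140 = 42 events. Coding the 60 as event-free gives 42/200 = 21%. Treating them as missing gives 42/140 = 30%.

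**4. Effect on a comparison, if one were made.** Assumptions: 100 per arm, two-sided 5% level, equal loss in both arms.

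| True rates | Unseen | Observed rates | Difference | Power |
|---|---|---|---|---|
| 40% vs 20% | 0% | 40% vs 20% | 20 points | 88% |
| 40% vs 20% | 20% | 32% vs 16% | 16 points | 76% |
| 40% vs 20% | 40% | 24% vs 12% | 12 points | 60% |
| 30% vs 15% | 0% | 30% vs 15% | 15 points | 72% |
| 30% vs 15% | 20% | 24% vs 12% | 12 points | 60% |
| 30% vs 15% | 40% | 18% vs 9% | 9 points | 46% |

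The risk ratio stays at 2 in every row.

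**5. Renal replacement therapy.** Section 2.0 gives a dialysis rate of 1–4% as background; it is not a one-year rate. If it is borrowed, 200 × 0.01 = 2 to 200 × 0.04 = 8 events. With 20% unseen, 1.6 to 6.4 remain. With so few events, one or two missed would be a visible share.

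**The case against.** The strongest reply is that nothing inferential is shown to depend on this. Section 10.0 names pain, depression and neurocognitive function for comparison, but not one-year admissions or renal replacement therapy. Its mention of dialysis use carries no time window and sits among the markers of acute kidney injury; endpoint 9 lists dialysis with ICU morbidities. The primary endpoints are creatinine change to postoperative day 2 and plasma F₂-isoprostanes/isofurans, and neither is touched. This stands, and it sets the priority.

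A reader might infer that patients cared for elsewhere are counted as event-free over a full year. The documents do not say so. They give no coding rule, and treating such patients as missing is equally compatible with the text. What can be said is that the rule is absent.

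A reader might also infer a biased treatment comparison. That would need different capture by arm. For example, with no true effect and 30% in both arms, capture of 80% versus 70% gives 0.24 − 0.21 = 3 points. Nothing in the documents suggests such a difference: the intervention is confined to the operating room, and patients and ICU staff are blinded.

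Three further limits stand. The call's list may not be exhaustive, and patients who die or cannot be reached will not be interviewed. A later chart note may record an outside event. For renal replacement therapy, sparse events are the main constraint: even 4% versus 1% with 100 per arm and perfect capture has only about 27% power (normal approximation).

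None of this supplies a source for outside admissions or dialysis, or a rule for unobserved patients.

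**Conclusion.** The point holds as a minor, inexpensive improvement to a secondary follow-up item. Following the plan as written, one-year admissions and renal replacement therapy treated at other hospitals may be missed, and the report could not distinguish no event from not observed.

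The size is unknown. The undercount equals the unseen share if unobserved patients are kept as event-free, and the documents give neither that share nor that coding. The 15–50% range and the 30% admission rate are assumptions, as is an equal event rate inside and outside the institution. With equal loss, the consequence is understated rates and attenuated absolute differences, while the risk ratio is preserved. The documents do not support a claim of bias between arms, or of any effect on the primary endpoints.

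**What to change.** - Add to the planned one-year call direct questions on any hospital admission and any dialysis since discharge, at any hospital, with dates.
- Define the one-year admission and renal replacement therapy outcomes as an event found in the institution's records or reported at interview.
- Report per arm how many patients were observed to one year or to death, by completed call or documented chart contact. Treat the others as missing and not as event-free. Because being observed is itself a post-randomization condition, these counts should accompany any rate.

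The cost is two or three questions in a call of about 15 minutes and a sentence or two in section 10.0. The downside is small: self-reported events carry some recall error and would not be confirmed by outside records.
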